Effects of concurrent activation potentiation induced by customized mouth guard on baseball and softball performance

Document Date: Feb 16, 2025

IRB approved date: Dec 20, 2023

Project summary

This study recruited 45 baseball and softball players, including 30 fielders and 15 pitchers. Using a randomized crossover experimental design, the study was divided into randomised divided into customised mouthguards trial (MG) and control trial (CON) without temporal positioning. After the participants wore the mouthguard, they performed the vertical jump and grip strength tests sequentially. At the end of the test, depending on the pitcher or fielder, a baseball pitching ability test or a hitting ability test was conducted using a radar baseball tracking system. It is expected to analyze the vertical jump height, grip strength, pitchers' straight and changeup ball speeds, rotation speeds, degree of displacement, on-base and off-base locations. Hitting ability was expected to be documented with respect to initial velocity, elevation, and consistency of elevation.

Key word: concurrent activation potentiation, athletic performance, bite force

Introduction

Concurrent Activation Potentiation (CAP) is a strategy that synchronizes voluntary contraction of remote and target muscles through remote voluntary contraction (RVC), resulting in an increase in contractile capacity of the target muscles, which in turn facilitates exercise performance (1). Possible physiological mechanisms contributing to CAP include increased alpha motor neuron activity, stimulation of myoclonic changes, motor cortical overflow theory, and inhibition of presynaptic inhibition. The most widely recognised theories are motor cortical overflow and inhibition of presynaptic inhibition (2). CAP can be achieved by using either single or multiple RVC muscle groups. The most commonly used muscle group is jaw clenching. The activation of the motor cortex area responsible for controlling the musculature of the jaw is known to trigger the activation or strengthening of the motor cortex area of the arms and legs, consequently leading to enhanced muscle contraction in these extremities (2).

Recent studies have indicated that the utilization of customized mouthguards may serve as an effective strategy to enhance the contraction of temporomandibular joint muscles, thereby improving the CAP effect (3). The use of customised mouthguards improves the CAP effect and enhances maximum isometric grip strength (4, 5), the force and height of vertical jump (4, 6-8), increases explosive power, muscle strength (3) and improves sprinting ability over short distances (8). It appears that the use of customised mouthguards may have an effect on improving the performance indexes of the explosive type of sports. However, there was no study that have examined the effects of using customised mouthguards on the performance of baseball pitcher.

For baseball pitchers, the fastball velocity and the sharpness of breaking ball are important indicators of pitching performance. For indicators of muscular strength and physical performance, excellent pitchers (e.g., MLB) generally have better indicators of these pitches, as well as better lower extremity explosive strength and upper extremity strength (9). However, the extent to which increasing the bite force through customized mouthguards can enhance the muscle strength and athletic performance of baseball pitchers remains to be investigated. The purpose of this study is to investigate whether the use of customised mouthguards is effective in improving the athletic performance of baseball and softball performance.

Methods

Study design

This study used a randomised crossover experimental design in which participants were randomised to complete a customised mouthguards trial (MG) and a control trial (CON)

without mouthguards. Participants were tested for grip strength, counter movement jump, and baseball pitching ability with (MG) or without mouthguards (CON). During the study, the participants maintained a training schedule of 6 days and 1 day of rest. The study was conducted on the next day after the seventh day off to avoid training or fatigue factors affecting the accuracy of the experiment.

Participants

25 professional baseball and softball players were recruited for this study. The inclusion criteria for this study were: (i) has won the top 8 national level baseball or softball championships in the last three years. (ii) no cardiovascular and joint diseases. (iii) aged 20 or above who are adults. (iv) continuing to train professionally more than 5 days a week for the past year. The exclusion criteria for this study were: (i) have not won the top 8 national baseball or softball championships in the past three years. (ii) have a cardiovascular or joint disease, or any injuries that may be impaired by exercise. (iii) participants who are underage or not in regular baseball or softball training. (iv) have injury to the temporomandibular joint. Prior to involvement in the study, participants are provided with a participant consent form to sign after receiving comprehensive information regarding the study and its potential risks. This study received approval from the Institutional Review Board of Jen-Ai Hospital - Dali Branch (202300083B0). All experiments were carried out in a covered playground stadium. This study was conducted following the Declaration of Helsinki.

Protocol

Approximately one month prior to the commencement of the experiment, participants were referred to a dentist for a dental diagnosis. A customized mouthguard was subsequently fabricated. All participants were required to perform the same test at least 2 times before the formal test to familiarize themselves with the content of the formal test. Participants were examined by a dental professional to check the alignment of the teeth, obtain the distribution of occlusal forces using a special occlusal plate, and make dental molds. After the customized mouthguards are completed, the test begins.

All tests began at 3:00 p.m., which is the baseball team's daily practice time. Participants recorded the first warm-up, including all dynamic stretches, sprints, and number of pitches, and performed the same warm-up in the next experiment. After a personalized warm-up, participants were randomly fitted with customized mouthguards (MG trial) or without mouthguards (CON trial), and tested for bite force, grip strength, counter movement jump and pitching test in sequence.

Outcome measure

Bite force was measured using a pressure-sensitive occlusion plate (GC Dental Prescale II) and subsequently scanned with a Bite Force Analyzer. Prior to the experimental phase, the subjects were familiarized with the protocol by first handling the plastic wrapping within the bag of the bite plate. They were then instructed to bite down with maximum force for a duration of ten seconds, thereby replicating the instructed scenario. The operator then selected the appropriate bite plate size (S, M, or L) and positioned it within the subject's oral cavity, replicating the initial procedure. The scanning process was conducted within approximately ten minutes with the bite plates stored in their original packaging to prevent light exposure during preparation and scanning. GC Prescale II bite plates were maintained in environments with controlled light and temperature (5°C) to ensure material stability.

In the grip strength test, the participant should stand with their feet separated to the width of their shoulders, their hands in a natural and unstretched position, and the grip strength meter (Smedlay's Hand Grip Dynamometer TTM, Japan) (10) held at the second knuckle. The researchers verbally reminded the participants to clench their jaws with all their strength while gripping the grip strength meter with all their strength. Participants were then performed two maximal grip strength tests with the dominant hand and the non-dominant hand, with a 1-minute break in between each test. The value is presented as the average of two sums of hands.

Jump height of counter movement jump was measured in this study using the SmartJump contact mat (Smartjump, Fusion Sport, Sumner Park, Queensland, Australia) measurement monitoring system (11). The participant assumes a standing posture on a mat with arms crossed, and is verbally prompted to clench their jaws and propel themselves upward with maximal force while simultaneously descending until their thighs are in a parallel position with the ground. Vertical jumps were performed three times, each time with a one-minute rest, and the average value of the three times was analyzed.

In this study, pitching ability was analyzed using Rapsodo pitching 2.0 (Rapsodo Baseball System, Rapsodo Inc, Fishers, IN) (12). After a full warm-up, participants were given a pitching test of 10 fastballs and 5 sliders. According to statistics data from Statcast Search website (https://baseballsavant.mlb.com/statcast_search), major league pitchers throw about 15 pitches per inning, including 61% fastballs and 39% breaking ball. Based on this data, the pitcher was asked to throw 15 pitches, including 10 fastballs and 5 sliders, with 15 seconds of rest between each pitch. Recorded ball speeds and

spin rates of fastballs and sliders for subsequent analysis.

Fabrication of mouthguards for participants

The customized mouthguard in this study was made by a professionally trained dentist. The impressions were made with alginate (GC Aroma Fine Plus Normal Set Alginate), following the manufacturer's guidelines to the best of our ability. The pouring was executed immediately after the impression was made with dental stone (GC Fujirock EP Type 4 Dental Stone) in accordance with the manufacturer's instructions and using a dental laboratory vibrator. The vibrator was utilized to eliminate air pockets within the dental stone, as these pockets have the potential to induce imperfections in the cast model.

The customized mouthguard was vacuum formed using a dental stone model as a mold. A thermoformed mouthguard material, copolyester (Keystone Pro-Form vacuum forming materials, 0.5 mm), was utilized to overlay the dental stone. The fabrication of MG in maximum intercuspal position involves the utilization of a dental stone cast derived from alginate, which is subsequently overlaid on top of the thermoformed material following a heating process (Figure 1).

Statistical Analysis

All data are presented as means \pm standard deviations. The Shapiro–Wilk test was employed to evaluate the normality of the data distribution. The bite force, grip strength, counter movement jump and pitching test were employed to analyses the through paired t-tests. Effect sizes were calculated using Cohen's d to quantify the magnitude of observed effects and defined as trivial (<0.20), small (0.20 – 0.40), moderate (0.40 – 0.80), and large (>0.8), respectively. The power value of each data was conducted using G*Power 3.1.9.6 software (13). All data were calculated using SPSS (version 20, Chicago, IL, USA), and the significance level was $p < 0.05$.

Reference

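### The protocol gives two numbers recruited, 45 and 25, and the hitting test in its summary is missing from Methods

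*Protocol*

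**What the plan says.** The Project summary gives the size and make-up of the sample: "This study recruited 45 baseball and softball players, including 30 fielders and 15 pitchers". It assigns the last test by role: "depending on the pitcher or fielder, a baseball pitching ability test or a hitting ability test was conducted using a radar baseball tracking system". It then names the hitting outcomes: "Hitting ability was expected to be documented with respect to initial velocity, elevation, and consistency of elevation".

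Methods differs. Under Participants: "25 professional baseball and softball players were recruited for this study". No split between pitchers and fielders follows. Study design lists grip strength, jump and pitching. The Protocol subsection says that participants were "tested for bite force, grip strength, counter movement jump and pitching test in sequence". Outcome measure describes bite force, grip strength, jump and pitching, and introduces the last of these with "participants were given a pitching test of 10 fastballs and 5 sliders". Statistical Analysis covers the same four: "The bite force, grip strength, counter movement jump and pitching test were employed to analyses the through paired t-tests". Hitting does not appear anywhere in Methods.

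**The concern.** The number of players and the set of tests are basic facts of a trial, and the protocol gives two accounts of each. Both sentences on recruitment are in the past tense and describe baseball and softball players in the same study. Neither is marked as superseded.

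A reader cannot tell whether 25 replaces 45, is part of it, or is an error. Nor can the reader tell whether hitting, which is the role-specific test for 30 of the 45 players in the summary, belongs to the study at all. When results appear, it will be impossible to judge from this document whether 20 players and three named outcomes were dropped, never enrolled or measured, or simply not reported. The number of pairs behind each comparison is uncertain for the same reason.

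**Working it through.** **Number recruited.** The summary's figure agrees with its own split: 30 + 15 = 45. Methods gives 25. The difference is 45 − 25 = 20 players, or 20/45 = 44% of the larger figure. The figure of 25 is neither 30 nor 15, so it cannot be the fielders alone or the pitchers alone as the summary counts them. The protocol gives no effect size, SD or target power, so neither 45 nor 25 can be derived from a sample-size formula, and that route cannot show which is meant.

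**Tests, section by section.**

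| Section | Bite force | Grip | Jump | Pitching | Hitting |
|---|---|---|---|---|---|
| Project summary | no | yes | yes | pitchers | fielders |
| Study design | no | yes | yes | yes | no |
| Protocol (test sequence) | yes | yes | yes | yes | no |
| Outcome measure | yes | yes | yes | yes | no |
| Statistical Analysis | yes | yes | yes | yes | no |

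**Who pitches.** The summary gives the pitching test to pitchers. The Protocol and Outcome measure subsections speak of participants without restriction. The same Outcome measure paragraph then speaks of the pitcher throwing the 15 pitches. Methods can therefore mean that all 25 players pitched, that all 25 were pitchers, or that an unstated number of pitchers among the 25 did so. If all 25 were pitchers, that conflicts with the summary's 15.

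**What the difference in number does to precision (illustration).** Assume a two-sided 95% interval for the mean paired difference and complete pairs. In units of the SD of the paired differences, the half-width is t(0.975, n − 1)/√n:

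- n = 45: 2.0154/√45 = 0.300
- n = 25: 2.0639/√25 = 0.413
- n = 15: 2.1448/√15 = 0.554

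For grip strength and jump, which both accounts give to every player, the ratio is 0.4128/0.3004 = 1.37, so the interval is 37% wider at 25 than at 45. For pitching, the summary's 15 gives 0.55 SD. Methods gives 0.41 SD only if all 25 players pitched; otherwise its pitching number is unknown and no comparison can be made.

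**The case against.** Four objections deserve weight.

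First, a reader might infer from "participants were given a pitching test of 10 fastballs and 5 sliders" that Methods assigns the pitching test to all 25 players, in direct contradiction of the summary's 15 pitchers. The text does not support that much. The same paragraph refers to the pitcher, and the Introduction frames the research gap around baseball pitchers. Methods is unclear on this point, and a pitching number of 25 is only one of its possible readings. This objection stands.

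Second, the interval widths are not figures that the protocol gets wrong. It plans means with SDs, paired t-tests and Cohen's d, with no confidence interval and no stated sidedness. The paired t-test is valid at any of these sizes, and there is no prospective sample-size calculation for either figure to break. This stands too: the widths show only what the discrepancy could mean, and no claim about power follows.

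Third, the absence of hitting from Statistical Analysis is weak evidence by itself, since a separate analysis plan may exist. That is fair. The point rests instead on the study design, the test sequence and the outcome measures, which are protocol content and contain no hitting procedure.

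Fourth, a summary is only an overview. An overview may leave out detail, but that does not explain a different number recruited or an additional test with its own outcomes.

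**Conclusion.** The contradiction is real and needs correcting. The protocol states 45 recruited in one place and 25 in another, a difference of 20 players that nothing explains. It announces a hitting test with three outcomes that Methods never describes. These conclusions rest on the text alone and need no assumption.

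Who takes the pitching test is unresolved, which is a lesser point than an outright conflict between 15 and 25. The 37% difference in interval width for grip strength and jump is illustrative and depends on a two-sided 95% interval and complete pairs.

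The documents do not show which number is right. A reader might also suspect that players or outcomes were dropped selectively. The protocol does not show that either; it only leaves the question impossible to answer.

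**What to change.** - Reconcile the Project summary and the Participants section to one number recruited, with its split between pitchers and fielders.
- If 25 is a subset of 45 or a reduced number, say so and account for the other 20 players.
- State which players take the pitching test, in the same terms in the summary, the test sequence and Outcome measure.
- Either give the hitting test a procedure, outcome definitions and an analysis in Methods, or remove it from the summary and state that it was not done.

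If the number recruited and the tests carried out are already settled, this costs only a correction of the text. If hitting is part of the study, its procedure and analysis must also be written.

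### Plain paired t-tests ignore the randomised test order, so any remaining period effect would cost precision and, with unequal orders, shift the mouthguard estimate

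*Protocol*

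**What the plan says.** Under Study design, the protocol describes a randomised crossover of a mouthguard (MG) and a control (CON) session. Its Protocol subsection says that, after warming up, "participants were randomly fitted with customized mouthguards (MG trial) or without mouthguards (CON trial"). No allocation ratio, blocking or other balancing of the two orders is given.

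The Statistical Analysis section names one test for all outcomes: "The bite force, grip strength, counter movement jump and pitching test were employed to analyses the through paired t-tests". It has no period, order or sequence term.

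The Methods do guard against practice and fatigue:
- Familiarisation: "All participants were required to perform the same test at least 2 times before the formal test".
- Warm-up: the first is recorded, and players "performed the same warm-up in the next experiment".
- Time of day: "All tests began at 3:00 p.m".
- Rest: "The study was conducted on the next day after the seventh day off to avoid training or fatigue factors".

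The sample size is 45 in the Project summary (30 fielders and 15 pitchers) and 25 under Participants. No SD, expected effect, target power or expected period effect is given.

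**The concern.** Because every test starts at the same hour, the two sessions must fall on different days. If each follows a rest day, at least one six-day training block lies between them. Form, motivation, conditions or residual learning may change over that time. Such a change raises the MG−CON difference for players who had CON first and lowers it for those who had MG first. A paired t-test cannot separate this from random variation between players. Two things are at stake:

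- **Precision:** the standard error grows.
- **The estimate:** if more players had one order than the other, the period effect does not cancel in the mean difference.

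The protocol itself treats training and fatigue as threats to accuracy, but its stated analysis has no step that would detect or remove what the design controls leave behind.

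**Working it through.** The protocol has no power or sample-size figure to reproduce, so the check starts from the crossover model.

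**Inputs from the protocol.** Two conditions in random order; paired t-test; 5% significance level; n = 15 (pitchers), 25 or 45.

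**Assumptions.** Two-sided test. Period effect π (session 2 minus session 1) of 0, 0.25, 0.5 or 1.0 SD of the paired difference. True effect τ set so that the paired t-test has 80% power at π = 0: τ = 0.778, 0.584 and 0.427 SD for n = 15, 25 and 45. Order is either unrestricted (an independent 1:1 draw per player) or balanced to within one player.

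**Model.** For player i, d_i = MG − CON = τ + s_i·π + e_i, with SD(e) = 1, s_i = +1 if CON came first and −1 if MG came first.

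**Paired t-test.** With n₁ CON-first and n₂ MG-first players:
- Shift of the estimate = π(n₁ − n₂)/n
- Inflation of the standard error ≈ √(1 + π²[1 − ((n₁ − n₂)/n)²])

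**Period-adjusted analysis.** Estimate = half the sum of the two order-group means of d; SE = ½·s_pooled·√(1/n₁ + 1/n₂); n − 2 degrees of freedom. The shift is zero.

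**Shift at π = 0.5.**
- 13:12 → 0.5 × 1/25 = 0.02 SD
- 15:10 → 0.5 × 5/25 = 0.10 SD
- 10:5 → 0.5 × 5/15 = 0.17 SD

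**Standard error at 13:12.** For π = 0.5: √(1 + 0.25 × 0.9984) = 1.12. For π = 0.25 and 1.0 it is 1.03 and 1.41.

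**Power** (paired: 200,000 simulated trials; adjusted: exact noncentral t, averaged over the splits):

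| Order | n | Paired, π = 0 | 0.25 | 0.5 | 1.0 | Adjusted, any π |
|---|---|---|---|---|---|---|
| Unrestricted | 15 | 80.2% | 77.7% | 71.0% | 50.0% | 76.5% |
| Unrestricted | 25 | 80.0% | 77.5% | 70.7% | 50.3% | 78.1% |
| Unrestricted | 45 | 79.9% | 77.5% | 70.6% | 50.6% | 79.0% |
| Near-balanced | 15 | 80.1% | 78.2% | 71.9% | 48.8% | 79.4% |
| Near-balanced | 25 | 80.1% | 78.0% | 72.4% | 49.9% | 79.8% |
| Near-balanced | 45 | 79.9% | 78.1% | 72.7% | 50.6% | 79.9% |

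The paired test's own loss is about the same whether or not order is balanced. The net gain from adjusting does depend on balance. At π = 0.25 and n = 15 it is 76.5 − 77.7 = −1.2 points with unrestricted order and 79.4 − 78.2 = +1.2 with near-balanced order. At π = 0.5 it is +5.5 to +8.4 and +7.2 to +7.5 points respectively.

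**Break-even π, above which adjustment gains power** (n = 15, 25, 45):
- Unrestricted: about 0.30, 0.22, 0.16 SD
- Near-balanced: about 0.14, 0.09, 0.04 SD

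**Type I error of the paired test.** Averaged over unrestricted order it is 4.9–5.1%. With near-balanced order at π = 0.5 it is 2.9–3.1%, which is conservative.

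**Chance of an unequal split if order was unrestricted (binomial).** 10:5 or worse at n = 15: 30%. 15:10 or worse at n = 25: 42%. 30:15 or worse at n = 45: 3.6%.

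**The case against.** The strongest reply is that nothing here is an error. Order is randomised, so the paired estimate is unbiased over the randomisation and the test holds its level; the shift belongs to the realised split and is not a systematic bias. Nothing in the protocol shows that a period effect exists. The players are established athletes, and familiarisation, the repeated warm-up, the fixed start time and the rest-day rule all work against one. A period effect of 1.0 SD has no basis in the document. With unrestricted order and 15 pitchers, adjustment loses power unless π exceeds about 0.30 SD. Silence on allocation is not evidence of simple randomisation, and a separate analysis plan could add an order check.

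Much of this stands. The test is valid, every π is assumed, the 1.0 SD column is an extreme and not an expected loss, and the larger splits are likely only if order was unrestricted. It does not remove the point. The protocol itself fixes the test, so this is a stated choice and not a detail left open. The controls reduce a period effect without excluding one. The order is known for each player by design, and ignoring it saves little when the orders are near-balanced.

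**Conclusion.** The concern holds as a cheap improvement to a valid analysis. If a period effect of 0.5 SD remains, the paired t-tests lose about 7–9 points of power from a nominal 80%. At 0.25 SD they lose about 2–3 points. An unequal split adds a shift of π(n₁ − n₂)/n, negligible at 13:12 and 0.10–0.17 SD at 15:10 or 10:5 when π = 0.5. For scale, the protocol's bands for Cohen's d change at 0.20 and 0.40, so a shift of that size could move a result across a band if d uses the SD of the differences, which the protocol does not specify.

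The conclusion rests on the assumed π, a two-sided 5% test, complete paired data and, for the chances of imbalance, simple 1:1 randomisation. Whether the analysed number is 25 or 45 hardly changes the paired test's loss; a small pitcher group makes marked imbalance more likely. Exact balance is impossible at 15, 25 or 45, but a split within one player makes the shift trivial.

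**What to change.** Analyse each outcome with treatment and period as fixed effects and participant as a random effect. With complete data this is essentially half the difference between the two order groups in their mean within-player period differences. Report the order split (MG first : CON first) and the estimated period effect with each result. If allocation is still open, state the method and assign order 1:1 in balanced blocks. If testing is complete, the recorded order is enough.

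The cost is a change of wording and one model term, available in the SPSS already named, with no extra participants or procedures. It uses one residual degree of freedom. With no period effect it costs 0.1–0.6 points of power under near-balanced order, or about 3.5, 1.9 and 1.0 points at n = 15, 25 and 45 under unrestricted order.
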